## 6. Potential Risks and Benefits

### 6.1 Risks

The principle potential risk to participants is the **breach of confidentiality**. Although we will make every effort to store data in a secure and confidential manner, and to use de-identified data, breaches of confidentiality may occur accidentally. In order to protect participant confidentiality:

- All data collection from families will be conducted either using HIPAA compliant or encrypted technology (i.e. EHR, EPIC patient portal, MyChart patient communication tool embedded in Epic, REDCap, and Act.MD) or through direct administration of measures per family preference.
- Only coded data will be sent by DotHouse to the study investigators. The investigators will keep a mastercode/ cross walk for all enrolled participants which will be kept separately from the coded data.

Additionally, because the research covers the topic of mental health and potential psychosocial stressors participation may be **emotionally distressing** to individuals in the study. Although we will strive to maximize the cultural sensitivity in delivery of the proposed intervention, it is possible that, among parents, their explanatory models of their child's condition will be incompatible with our proposed intervention and even assessments. There is also the possibility that a concern of child abuse or neglect and the identification of suicidal or homicidal risk may be disclosed. Although we do not believe that these are direct risk or adverse events related to the intervention, we believe that they are important to anticipate and address. This has the potential to upset study participants. In order to address the potential for upsetting events potentially related to participation:

- We will make every effort to hire bicultural and bilingual (Spanish and Vietnamese) family partners in order to ensure that all families receive clear information about FN, their referral plan options and can adequately share their preferences and explanatory models of their child's needs.
- FP and all staff will be fully trained by the PIs and FN supervisor on how to work with children and families, including working with the families of children with behavioral health care needs, as well as the protocol for managing mandated reporting procedures for concerns of child abuse and management of emergency situations including suicidal or homicidal Ideation (see page 11, Section 10.2 Concerns about Abuse, Neglect, and Suicidality). In these situations the FP and staff will let the mandated reporters (PIs and responsible clinical staff at the health center) if such a concern is identified at the health center during routine encounter) know of these concerns/ emergencies in order to allow for appropriate management.
- Families will clearly be informed that they have the right to decline receiving FN services and still be able to continue their other clinical services at DotHouse without negative consequence.

### 6.2 Potential Benefits

The potential long-term benefits of this study plan outweigh its risks. All children who demonstrate behavioral health symptoms during screening OR whose parents express a concern will have the opportunity to receive services that exceed those currently provided. The FN support, which will be available to all participants, will likely assist the child and their family in coordinating and accessing appropriate behavioral health services. Specifically, children receiving FN services could benefit from screening and early identification of symptoms, working with the family partner and through the FN

supports, psycho-education, care coordination, access to and engagement with behavioral health services.

### 6.3 Analysis of Risks in Relation to Benefits

Subjects could directly benefit from FN and accessing behavioral health services. We believe the potential benefit outweighs the individual risk in this study.

## 7. Study Subject Selection

### 7.1 Subject Inclusion Criteria

We will be enrolling parent-child dyads and in the cases where more than one child is eligible parents can enroll all eligible children. Eligibility criteria are defined as:

- Children ages 3-12 years who screen positive on the Survey of Wellbeing of Young Children (SWYC) (3-5 years) OR Pediatric Symptom Checklist-17 (PSC-17) (6-12 years) OR whose parents indicate a behavioral health concern during any pediatric visit. These screens are conducted at every well-child visit as standard practice. They are embedded in EPIC and results recorded in the child's EHR. We include concern because data from minority and low income populations has shown that parental concern in combination with a screening tool can provide critical information about a child's mental health.
- We will enroll children and parents regardless of language. Both the PSC-17 and SWYC are available in multiple languages including Spanish and Vietnamese. As we have in previous studies, we will use telephonic translation services as needed (for languages other than English, Spanish or Vietnamese). We have selected this specific age range (3-12 years) because we believe our FPs are well qualified to work with this group for two reasons: 1) our FPs have experience interacting with the school systems and children in this age range are served by the school systems (as opposed to children <3 who may be served by Early Intervention).

### 7.2 Subject Exclusion Criteria

Parent-child dyads in which the child meets any of the following criteria will be excluded from participation in this study:

[figure not shown]
- Children who are already actively engaged in behavioral health specialty care services for which they are being referred, (e.g. a family may not be referred for behavioral health therapy if they are actively engaged in these services in the past 30 days) , children with active psychosis, or children with safety concerns requiring emergency mental health services. They *may* be referred if they are in need of *additional, new services* like school services.

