## 4.2 Study Outcome Measures (See Table 1)

### 4.2.1 Primary Outcome Measures

#### Objective 1: To identify the most effective strategy to deliver FN

**Our primary outcome measure is receipt of behavioral health services within 90 days (yes/no)** will be defined as first encounter with behavioral health services within 90 days of randomization obtained from the electronic health record including Family Partner's template documentation.

Related to this primary objective, we will evaluate *time-to-receipt of behavioral health services* defined as time from randomization to first behavioral health service encounter obtained from the electronic health record, including family partner's template documentation. Dates will be obtained from administrative and billing data (electronic health records) for services within DotHouse, and FP documentation for services outside the health center.

A second primary outcome includes change in child symptoms over time.

- Pediatric Symptom Checklist-17 (PSC-17). A 17-item psychosocial screen designed to recognize cognitive, emotional, and behavioral problems. Three subscale Internalizing, Attention, and Externalizing have specific cutoffs and provide additional guidance regarding need for further follow-up. PSC-17 is embedded in the Epic (electronic health record) as a self-scoring form. It is widely used and has been validated in diverse populations.
- The Survey of Wellbeing of Young Children (SWYC). The SWYC screens for cognitive, motor, language, and social-emotional development among children up to 5½ years of age. We will track behavioral symptoms using the SWYC's Preschool Pediatric Symptom Checklist (PPSC), an 18-item questionnaire that has demonstrated strong concurrent validity with the Child Behavior Checklist (CBCL) and parents' reports of socio-emotional diagnoses as well as acceptability in diverse populations. Translations are available in a range of languages and the SWYC is currently being incorporated into the Epic system used at DotHouse.

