**Table 1. Primary and Secondary Outcomes**

	Outcome	Description	Measurement Source	Timing
Primary	Time to services	Time from randomization to first behavioral health service encounter	Electronic health record including FP's template documentation	90 days
	Access to services	1 st encounter with behavioral health services within 90 days of randomization	Electronic health record including FP's template documentation	90 days
	Child symptoms	Score on PSC-17 and SWYC	Measures will be sent to families via Epic's mobile app MyChart or administered by Zoom/telephone in REDCap or sent to the parent by mail	Baseline 3, 6, 9, & 12 mo
Secondary	Retention in services	≥4 visits or resolution of service need for families receiving psychotherapeutic or psychopharmacological services	Electronic health record including FP's template documentation	90 days
	Patient Satisfaction	HCQ & PSN-I	Measures will be sent to families via Epic's mobile app MyChart or administered by Zoom/ telephone in REDCap or sent by mail	6 mo
	Qualitative Parent Interviews	Parent interviews to describe the effect of cultural and linguistic concordance between patients and FN.	Interview completed through Zoom/phone and audio recorded, stored in HIPPA compliant BOX drive.	6 mo
	Qualitative DotHouse Staff Interviews	DotHouse staff interviews to understand their perspective in the implementation of family navigation (work flow changes etc).	Interview completed through Zoom/phone and audio recorded, stored in HIPPA compliant BOX drive.	ongoing

Note: The PSC-17 is currently administered to children at pediatric well visits at DotHouse as part of usual care. Plans are to implement the SWYC in summer/fall of 2018. Both tools have been used extensively and research supports use for symptom monitoring.

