**Because some families will be referred for a behavioral health visit without referral to a FP, but may in fact benefit from a visit with an FP based on assessment by the behavioral health clinician, we will allow for the behavioral health provider at DotHouse to refer to the study. This provider will also be able to follow either Pathway 1 or Pathway 2 as described above. Any member of the child's care team may refer to the FP**

**Initial contact with FP.** As much as feasible, the FP will meet with the child and family during the visit. If the FP is not available (e.g. evening/weekend visits,) the initial contact will be via telephone. During this visit/contact, the FP will describe this research study, including randomization to different study conditions, and obtain consent. The FP will obtain written consent and HIPAA authorization for all in-person meeting. The FP will obtain verbal consent for both study participation and HIPAA authorization when the initial contact is by telephone. (See INSPIR for further detailed description of recruitment, consenting, and randomization procedures.)

Families who decline participation in the study will have the option to work with health center care managers (instead of the study FPs) who also offer care coordination. Those families will not be randomized or followed as part of the study.

If during the discussion with the FP, the parent states that s/he is interested in the study but not interested in seeking behavioral services at this time, the FP will ask the parent if she can reach out to them in ~ 3 months to see if services for the child are desired at a later date. If upon recontacting the

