## 11.2 Source Documents

This study includes data collection and management tools that also meet HIPAA security rules to protect confidentiality and security of protected health information.

**Electronic Health Record (EHR):** Data will be abstracted from the EHR of children including diagnoses (from the child's problem list), basic demographic data, and information on scheduled appointments, missed appointments, screening tools administered, screening results, referrals made, referrals completed, billing codes, and surveys collected through MyChart, the EHR's patient portal. MyChart is an interactive system integrated into the patient EHR (Epic/ OCHIN) and offers patients personalized and secure on-line access to portions of their medical records and also allows providers to send messages and to communicate with patients. MyChart will be used to communicate with families, conduct screening, and monitor symptoms, and track study outcomes / measures. Epic/OCHIN is a fully encrypted, HIPAA compliant system. EHR records at the health center are further protected by firewall

technology. The study investigators will only receive de-identified, ID coded MyChart collected data from DotHouse.

All data will be provided by DotHouse to the study investigators in ID coded form.

FP visit templates: FPs will document in the EHR the details of the eight tasks outlined in protocol manuals: 1) initial encounter, 2) assessment of barriers, 3) plan to address barriers, 4) referrals to service (type and location) 5) confirming appointments scheduled, 6) confirming appointments attended, 7) post-assessment follow-up, and 8) connecting with treatment services. De-identified logs will be scored by study staff to measure the number and nature of completed tasks by the FP.

BACO billing data: We will triangulate BACO billing data with EHR data documenting service use. BACO data will allow us to capture behavioral health services provided outside of DotHouse. BACO billing data will be de-identified by staff at DotHouse who are responsible for maintaining the cross walk between patient name and study ID.

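### The primary outcome counts any behavioral health encounter within 90 days, so a child enrolled for an additional service can score through one already in use, which dilutes all factor effects

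*Combined protocol and SAP*

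**What the plan says.** **Eligibility.** Section 7.2 excludes "Children who are already actively engaged in behavioral health specialty care services for which they are being referred". Its example is a family that may not be referred for therapy "if they are actively engaged in these services in the past 30 days". It then makes an exception: "They *may* be referred if they are in need of *additional, new services* like school services". The exclusion is thus specific to the service being sought.

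**Outcome.** Section 4.2.1 defines the yes/no primary outcome as "first encounter with behavioral health services within 90 days of randomization obtained from the electronic health record", supplemented by Family Partner (FP) template entries. Table 1 repeats this and defines time to services as "Time from randomization to first behavioral health service encounter". Neither place requires the encounter to be with a new or referred service.

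**Analysis.** Section 12.3 mentions services designated as primary at the initial visit, but only when it introduces later multilevel models for several services per child. Current service use is not among the baseline characteristics listed in 12.3, nor among the example minimization variables in Sections 5 and 9.

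**Data.** Section 11.2 says the FP templates record the type and location of referrals and whether appointments were attended. It also plans to compare billing data with the health record.

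**The concern.** The trial's aim is access to services. A child in regular therapy may enrol to obtain, say, school services. Under the written outcome, that child's next recorded therapy visit after randomization is a success, whether or not the school service is ever obtained and whichever factor levels were assigned. Such children add equally to both levels of every factor. They raise the reported access rate, shorten time to receipt and shrink each contrast. Ongoing visits could also count toward the four-visit retention outcome in 4.2.2.

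In an optimization trial the cost of dilution is that a useful delivery component may look ineffective and be left out of the final package.

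**Working it through.** **Inputs.** From Section 12.2: 60% in the core condition, 75% with a delivery strategy, two-sided 5%, 304 families. Power for this outcome is not stated; 80% is assumed. Each main effect compares half the families with the other half, 304 / 2 = 152 per level. The share f of index children with an ongoing service is not given, so a range is used.

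**Step 1: reproduce the plan's figure.** With pooled variance under the null and no continuity correction:

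n per level = [1.960 × √(2 × 0.675 × 0.325) + 0.842 × √(0.60 × 0.40 + 0.75 × 0.25)]² / 0.15² = (1.298 + 0.550)² / 0.0225 ≈ 152, total 304.

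This matches exactly, and power at 152 per level is 80.0%.

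**Step 2: dilution.** Suppose 60% v 75% applies to children without ongoing care, and the others succeed at both levels. Then p1 = f + (1 − f) × 0.60, p2 = f + (1 − f) × 0.75, and the difference is 0.15 × (1 − f).

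| f | Core | Enhanced | Difference (points) | Odds ratio | Power at 152 per level | Total N for 80% |
|---|---|---|---|---|---|---|
| 0 | 60.0% | 75.0% | 15.0 | 2.00 | 80.0% | 304 |
| 5% | 62.0% | 76.3% | 14.3 | 1.97 | 77.0% | 328 |
| 10% | 64.0% | 77.5% | 13.5 | 1.94 | 73.7% | 356 |
| 20% | 68.0% | 80.0% | 12.0 | 1.88 | 66.6% | 418 |
| 30% | 72.0% | 82.5% | 10.5 | 1.83 | 58.9% | 500 |

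**Step 3: incomplete attendance or capture.** If only 80% of children with ongoing care have a recorded visit, at both levels alike, then p1 = 0.8f + (1 − f) × 0.60 and p2 = 0.8f + (1 − f) × 0.75. The difference is still 0.15 × (1 − f). Power is 72.1% at f = 10% (62.0% v 75.5%) and 62.8% at f = 20% (64.0% v 76.0%).

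**Step 4: what the 60% and 75% refer to.** Section 12.2 takes the 60% from prior work and does not describe that population, so two other readings are possible.

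- Both rates already include children with ongoing care. Then 304 and 80.0% stand, and the rates implied in the remaining children are (0.60 − f) / (1 − f) and (0.75 − f) / (1 − f): 55.6% v 72.2% at f = 10%, 50.0% v 68.8% at f = 20%.
- Only the 60% includes them, and the relative risk of 1.25 applies to the rest. Then p2 = f + 1.25 × (0.60 − f) = 0.75 − 0.25f. Power is 63.6% at f = 10% (60% v 72.5%) and 44.7% at f = 20% (60% v 70%).

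**The case against.** **An index service was probably intended.** Section 12.3 speaks of appropriate services and of those designated as primary, and Appendix A lists the first appointment after the referral. This is fair as evidence of intent. It does not change the outcome definition, which staff abstracting the data would have to follow as written.

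**Capture is not certain.** Section 4.2.1 takes dates for outside services from FP documentation, and the FP templates follow the FP's own referrals. Section 11.2 brings in billing data without giving it a role in the primary outcome. An ongoing outside visit may never be counted. This stands: a reader might infer that every such child is an automatic success, but the documents support only that the child can score through a recorded visit.

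**The bias is conservative.** Dilution of this kind favors no factor level and does not inflate type 1 error. On the odds-ratio scale of the planned logistic model the shift is modest, from 2.00 to 1.88 at f = 20%. This stands too; the cost is lost power and a blurred meaning.

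**Section 9 does not establish a pool of ongoing-care patients.** It states that "we will allow for the behavioral health provider at DotHouse to refer to the study", and a reader might infer that clinicians will send children they already treat. The sentence concerns families sent for a behavioral health visit without an FP referral, whose need is recognized at the clinician's assessment. It describes missed referrals and does not mention established patients, and 7.2 still applies to them.

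**Tying the outcome to referrals has its own risk.** FPs run the assignment program, deliver the condition and record the referrals. An outcome resting on their entries alone could be misclassified differently by condition. This is a valid caution and shapes the fix.

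**Conclusion.** The mismatch is real: eligibility is tied to a service and the primary outcome is not. Followed as written, the outcome rule can count continuing care as new access in children whom 7.2 expressly admits, and it pulls all factor effects toward the null.

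The size is unknown because f is not in the documents. The power figures of 77.0% to 58.9% for f = 5% to 30% rest on two assumptions: that 60% v 75% describes children without ongoing care, and that the others succeed at both levels. If the planned rates are all-inclusive, no power is lost, although the outcome still mixes continuation with access. A reader might infer that the trial is shown to be underpowered or that 304 is miscalculated. Neither follows: 304 reproduces exactly, and f may be small. The definition should be corrected, but the mismatch does not invalidate the design.

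**What to change.** In 4.2.1 and Table 1, define the event as the first attended encounter with a behavioral health service for which the child was referred at or after enrolment. Include services chosen later in the service plan described in Section 9. Do not count continuation of a service in which the child was already actively engaged at randomization. State that a single assessment by the referring clinician does not make that service ongoing; otherwise a child who then starts care with that clinician would be scored a failure despite real access.

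Apply the same definition to time to receipt. Record active service use before randomization, include it as a covariate in the models, and report the any-encounter version as a sensitivity analysis. Say in 12.2 which population and which definition the 60% and 75% describe; if they hold for the new definition in all enrolled children, 304 again gives 80.0%.

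The cost is some wording, one baseline item and a rule-based step that matches encounters to referrals. That step should be done blinded to condition and checked against health-record and billing data, because FPs who know the assignment record the referrals. The templates already hold referral type, location and attendance. Eligibility and the intervention do not change.

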## 8. Study Intervention: Family Navigation

Family navigation (FN) is care management designed to address barriers to services – in our study, behavioral health services. In this study, the core FN intervention will be delivered to all participants by study Family Partners (FP), a paraprofessional community member who is trained to support families of children with behavioral health. FN strategies to be tested will be delivered. Literature strongly supports the hypothesis that initiation of behavioral health services is directly influenced by several key domains, including: parents' motivation and capacity to pursue services (e.g., health literacy, mental health), families' resources and competing demands on their time, and healthcare system factors, such as difficulties scheduling timely appointments and barriers to communication. Core FN components (see Figure 4) are designed to address these domains. For example, motivational interviewing is included

to increased parents' motivation to pursue services. Problem-solving strategies are introduced to improve parents' capacity to pursue services, and education addresses health literacy. Assistance with social determinants of health is essential for reducing competing demands on families' time (e.g., help with housing, benefits). Care coordination is focused on healthcare system factors and is designed to promote an activated care team. The components of the core navigation intervention, which all participants will receive, are described below.

Of note, the core FN intervention exceeds the current standard of care at the health center. Dothouse

employs care managers who assist families access behavioral health services and meet concrete resource needs. However, care managers are not routinely involved with all children with behavioral health concerns and they do not support engagement longitudinally.

- Universal Screening and Behavioral Health Referral. As described above, The FN intervention begins with a family-centered response to a positive behavioral health screening or parent report of a concern. The FP will provide psychoeducation and use MI to explore family preferences regarding further evaluation, and referral to behavioral health services.
- Support for Access to Behavioral Health Services. The FP will work with the family after referral from the pediatric clinician to access recommended services, support family preferences, and engagement in treatment through the creation of a Family Plan. FPs will employ problem solving strategies to assist families to resolve logistical barriers, MI to address hesitancy to engage in services, and provide care coordination including with schools and other providers.
- Engagement in evidence-based treatment. FN aims to support family adherence to the recommendation for further behavioral healthcare. The FP, who is trained in motivational interviewing and collaborative decision making, will use these skills to explore parental response to any identified concerns, with the goal of supporting parental engagement in the referral process and behavioral health treatment plan.
- Monitoring to achieve family goals. Active FN will continue until the goals articulated in the Family Plan have been achieved, at which point the FP will be available on as needed basis for up to 12 months.
- Family strengthening. FNs will refer families to local support groups and parent mental health services if needed.
- Connection to concrete resources: FPs, who will receive extensive training on available local resources and entitlements, will connect families to community-based resources (e.g., disability insurance, utility discounts).

We will test 4 FN delivery components in a highly efficient experimental design. Families will be randomized to one of eight combinations of components that will be delivered by FPs. The following is a description of the specific components.

**Strategy A: Core FN v. Enhanced: Technology assisted.** In core FN, FPs keep records and communicate with families using standard information technology, including telephones, electronic medical records, and standard desktop software. In the enhanced condition, FPs will also have access to Act.MD, a cloud-based care coordination and communication tool that offers the potential to improve communication with families, schools, and the primary care site through administration of online questions, videoconferencing, and common portals that can be used by parents and multiple providers (e.g., FP, pediatrician, teacher). Families randomized to have access to Act.MD will work with the FP to become familiar with the features of this technology. The FP will demonstrate how to set up the program on a SMART phone and a computer. She will obtain permission to reach out to school personnel in accordance with FERPA guidelines to introduce this technology to relevant school staff – e.g. the child's teacher or counselor. The FP will work collaboratively with the child's family and care team to determine how to utilize Act.MD to support the child and the family's goals. These features will incur additional costs for licensing fees and staff time, but we hypothesize it will also improve cross system collaboration and engagement with services.

**Strategy B: Clinic-based v. Enhanced: Clinic + Community.** In core FN (i.e. Clinic-based), FPs will be restricted to working at the primary care clinic - communication will be restricted to telephone, text, and clinic visits. In the enhanced condition, FPs will be available to meet families in their home and community, and accompany families to community-based meetings at school or childcare (IEP meetings, parent-teacher conferences, meetings with in-home behavioral health providers) . While out-of-clinic visit may substantially increase costs due to the FP's travel (time and mileage), we hypothesize it will also improve engagement with services.

**Strategy C: Pediatric Surveillance v. Enhanced: Tracking at 3, 6, 9, and 12 months.** In core FN (i.e. Pediatric Surveillance at well-child visits), monitoring is determined by standard pediatric practice. In Massachusetts, behavioral screening is mandated at every pediatric visit, which for children in the target population (ages 3-12 years) is annually. In experimental conditions with "enhanced monitoring," FPs will screen children using validated instruments quarterly (SWYC, PSC-17 based on age) and communicate results to the child's care team. The screening tools will be deployed through MyChart , the EPIC EHR patient portal. Results feed directly into the child's record. Screening tools may also be deployed through REDCap or mailed to the parent in a sealed envelope with a stamped and addressed return envelope inside. Once the mailed parent measures are received by research staff at Boston Medical Center, they will be manually entered into RedCap and the paper copies will be stored in a locked filing cabinet in a locked office. The FP will be responsible for initiating and tracking the screening. She will message the child's PCP when new screening results are available and communicate with the PCP and care team regarding any changes in symptoms. We expect additional costs of increased monitoring to be modest, and that the additional information will allow care to be better aligned with children's symptomatology and, thus, lead to improved engagement with services.

**Strategy D: tailored vs standardized, schedule-based visits with families.** Families who receive tailored visits, will work with their FN on addressing issues as they arise. They will not have any pre-specified schedule for visits or contacts. Families who received standardized scheduled visits, will have a pre-specified schedule of visits. This will include monthly contacts with families for 6 months. Each contact will have a specified agenda which includes review of family goals, and a topic (e.g. what is an individualized education plan) to review.

Regardless of the combination of delivery components to which families are randomized (core or enhanced strategies), families will core FN elements.

